9 APPENDICES

Appendix I Details for Co-primary and Secondary Endpoints

A stratified Finkelstein and Schoenfeld Joint Rank Test will be used for the co-primary efficacy endpoint of change from baseline in 6-MWD at 18 months. Pairwise comparison of patients to determine their ranking will be performed using the following steps:

Step 1: Comparison based on time to death

Definition of time to death: Time from date of first dose of study drug to death (months) will be calculated as: (date of death – date of date of first dose of study drug + 1)/30.4. If a patient did not die, time from date of first dose of study drug to death (censoring time) will be calculated as: (date of last study visit –date of first dose of study drug+1)/30.4. Time from date of first dose to death will allow values up to Month 18 analysis visit.

Comparisons can be made if:

- Both patients died and there is no tie in the survival time
- One patient died and the other patient did not die and the time of the death for the patient that died was ≤ the time to death for the patient that did not die (censoring time).

Comparison will be inconclusive if:

- Both patients died and the time to death is a tie
- Both patients were alive
- One patient died and the other patient did not die, and the time of death for the patient was > the time to death of the patient that did not die (censoring time).

Step 2: Comparison based on time to loss of ability to perform 6-MWD

Definition of time to loss of ability to perform 6-MWD:

Loss of ability will be indicated if any of these scenarios occur:

- A patient could not perform the test without an additional walking aids compared to the walking aid used at the screening visits
- A patient could not perform the test without an increase in oxygen flow compared to the oxygen flow used at the screening visits.
- If at a scheduled study visit the patient was unable to perform the test due contraindications (such as: unstable angina within the last month, myocardial infarction within the last month, resting heart rate>120 beats a minute, systolic blood pressure>180 mmHg, diastolic blood pressure>100 mmHg, hospitalization within 2 weeks or other reasons specified (eg, wheelchair)).

Version: 1.0

Alnylam Protocol No. ALN-TTRSC-004

The time of loss of ability to perform 6-MWD will be based upon the analysis visit. A patient may have more than one onset time for loss of ability to perform 6-MWD during the study. For a patient with more than one scheduled visit where the patient was unable to perform the test, the time of loss will be at the visit where the patient lost and never regained the ability to walk. For a patient not considered to have lost the ability to walk, the time from loss of ability (censoring time) will be calculated as: (date of the latest 6MWD – date of first dose +1)/30.4. Time from first dose to loss of ability will allow values up to Month 18 analysis visit. Note: Any patient that is able to perform the walk at Month 18 visit will be considered a censored patient.

Comparison can be made if:

- Both patients indicated a loss of ability and there is no tie in the time to loss (scheduled visit)
- One patient indicated a loss of ability and the other did not, and the time of the patient who lost the ability to perform the test was \leq the time of the patient who did not lose the ability to perform the test (censoring time).

Comparison will be inconclusive if:

- Both patients indicated a loss of ability and there is a tie in the time to loss (scheduled visit)
- Both patients did not indicate a loss of ability
- One patient indicated a loss of ability and the other patient did not, and the time of the patient who lost the ability to walk > the time of the patient who did not lose the ability to walk (censoring time).

Step 3: Comparison based on change from baseline in 6-MWD

Definition of change from baseline in 6-MWD: Change in 6-MWD (meters) from baseline will be calculated as: (distance walked at post-baseline visits - distance walked at baseline). Baseline will be defined as stated in section 6.1.

To compare change from baseline in 6-MWD (meters) for a pair of patients, the latest common postbaseline study visit that both patients had 6-MWD measurements will be compared. In the event that the change in distance walked from baseline between the pair of patients is identical, a score of 0 (inconclusive) will be assigned to both patients.

Additional details:

- If a patient had > 0 meters for 6-MWD at month 18 and the patient died within month 18 analysis window, then the patient will be considered unable to perform 6-MWD at month 18.
- If a patient did not have any post-baseline information (eg, no information on survival status and no post-baseline data regarding 6-MWD), then the patient will be inconclusive for all comparisons.

Prior to the database lock, data collected from the 6-MWD test will be carefully reviewed to identify unexpected scenarios.

Version: 1.0

Alnylam Protocol No. ALN-TTRSC-004

Version: 1.0

Alnylam Protocol No. ALN-TTRSC-004

C-004

Date of Issue: 21 October 2015

Secondary endpoint: Composite CV Mortality and CV Hospitalization

Step 1: Comparison based on time to CV mortality

Definition of time to CV mortality: Time from date of first dose of study drug to CV death (months) will be calculated as: (date of death due to CV – date of first dose of study drug + 1)/30.4. If a patient did not die due to CV, time from first dose of study drug to CV death (censoring time) will be calculated as: (date of last study visit/date of death not due to CV – date of first dose of study drug+1)/30.4. Time from first dose of study drug to CV mortality will allow values up to Month 18 analysis visit.

Comparisons can be made if:

- Both patients died due to CV and there is no tie in the survival time
- One patient died due to CV and the other patient did not die due to CV and the time of the CV mortality ≤ the time to CV mortality for the patient that did not die (censoring time).

Comparison will be inconclusive if:

- Both patients died due to CV and the time to mortality is a tie
- Both patients died (not due to CV)
- Both patients were alive
- One patient died (not due to CV mortality) and one patient was alive
- One patient died due to CV and the other patient did not die due to CV, and the time of CV mortality was > the time to CV mortality of the patient that did not die (censoring time).

Step 2: Comparison based on number of CV hospitalizations

Definition of number of CV hospitalizations: For each patient, the cumulative number of CV hospitalizations will be tabulated starting from the date of the first dose of study drug until up to Month 18 analysis visit.

To compare the number of CV hospitalizations for a pair of patients, the total number of CV hospitalizations up to the latest common time on study will be compared. In the event that the total number of CV hospitalizations is identical between the pair of patients, a score of 0 (inconclusive) will be assigned to both patients.

Date of Issue: 21 October 2015

Secondary endpoint: Change in NYHA from Baseline

Step 1: Comparison based on time to death

This comparison will use the same assumptions as stated for the co-primary endpoint.

Step 2: Comparison change in NYHA class from baseline

Definition of change in NYHA class from baseline: Change in NYHA class from baseline is defined as: (NYHA class at post-baseline visit – baseline NYHA class). Baseline will be defined as the latest NYHA measurement prior to study drug. The possible range of values for change in NYHA is +3 (deterioration in health status) to -3 (improvement in health status). A positive change would indicate deterioration in health from baseline and a negative change would indicate an improvement in health from baseline.

The possible values of NYHA class at a visit are as follows:

- Class I coded as 1
- Class II coded as 2
- Class III coded as 3
- Class IV coded as 4

To compare the change in NYHA class from baseline for a pair of patients, the latest common post-baseline study visit that both patients had a non-missing NYHA result will be compared. In the event the change in NYHA from baseline between a pair of patients is identical, a score of 0 (inconclusive) will be assigned to both patients.

Additional details:

• If a patient did not have any post-baseline information (eg, no information on survival status and no post-baseline data regarding NYHA), then the patient will be inconclusive for all comparisons.

Version: 1.0

Alnylam Protocol No. ALN-TTRSC-004

Secondary endpoint: Change in overall summary score (KCCQ) from Baseline

Step 1: Comparison based on time to death

This comparison will use the same assumptions as stated for the co-primary endpoint.

Step 2: Comparison change in overall summary score from baseline

Definition of change in overall summary score from baseline: Change in overall summary score from baseline is defined as: (overall summary score at post-baseline visit – baseline overall summary score). Baseline will be defined as the latest overall summary score measurement prior to study drug. The possible range in change in overall summary score is -100 (deterioration in health status) to +100 (improvement in health status). A negative change would indicate deterioration in health from baseline and a positive change would indicate an improvement in health from baseline.

To compare the change in overall summary score from baseline for a pair of patients, the latest common post-baseline study visit that both patients had a non-missing overall summary result will be compared. In the event the change in overall summary score from baseline between a pair of patients is identical, a score of 0 (inconclusive) will be assigned to both patients.

Additional details:

- If a patient did not have any post-baseline information (eg, no information on survival status and no post-baseline data regarding overall summary score), then the patient will be inconclusive for all comparisons.
- If a patient had a missing baseline overall summary score and did not die, then the patient will be inconclusive for all comparisons.

CONFIDENTIAL

Version: 1.0

Alnylam Protocol No. ALN-TTRSC-004

Date of Issue: 21 October 2015

Secondary endpoint: CV Mortality

[figure not shown]
Definition of time to CV mortality: Time from first dose of study drug to CV death (months) will be calculated as: (date of death due to CV – date of first dose of study drug + 1)/30.4. If a patient did not die due to CV, then time from first dose of study drug to CV death (censoring time) will be calculated as: (date of last study visit/date of death not due to CV – date of first dose of study drug+1)/30.4. Time from first dose of study drug to CV mortality will allow values up to Month 18 analysis visit.

[figure not shown]
Secondary endpoint: All-cause Mortality

Definition of time to all-cause mortality: Time from first dose of study drug to all-cause death (months) will be calculated as: (date of death (any reason for death) – date of first dose of study drug + 1)/30.4. If a patient did not die, then time from first dose of study drug to all-cause mortality (censoring time) will be calculated as: (date of last study visit – date of first dose of study drug+1)/30.4. Time from first dose of study drug to all-cause mortality will allow values up to Month 18 analysis visit.

Version: 1.0

Alnylam Protocol No. ALN-TTRSC-004

Version: 1.0

Alnylam Protocol No. ALN-TTRSC-004

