- t The 6-MWT will be conducted twice during the Screening/Baseline visit (practice and actual test to be performed at least 1 hour apart) and both tests must be completed within 28 days of Day 0. The assessments will include pre- and post-walk assessment of O₂ saturation, blood pressure, heart rate, and the Borg scale ratings for fatigue and dyspnea. The higher of the 2 values at Screening/Baseline will be used for eligibility purposes. The 6-MWT will be conducted only once, prior to dosing, at all subsequent time points.
- u An ECHO done at Screening/Baseline and for all subsequent time points will be evaluated by a central laboratory.
- v Cardiac MRI with late gadolinium enhancement (LGE) is only to be obtained in patients without contraindications (i.e., pacemakers, defibrillators, inadequate renal function or allergy to gadolinium) at selected sites on a subset of patients (up to 60). All time points will be evaluated by a central lab.
- w ^{99m}Tc scintigraphy by 3D SPECT during the study is an exploratory assessment and is not intended for diagnostic purposes or to fulfill eligibility criteria for the study. Either ^{99m}Tc pyrophosphate (^{99m}Tc-PYP) or ^{99m}Tc-3,3-diphosphono-1,2-propanodicarboxylic acid (^{99m}Tc-DPD) can be used as a tracer. The tracer should not be changed for the patient during the study. This assessment will only be performed at selected sites on a subset of patients (up to 60). All time points will be evaluated by a central lab.
- x This assessment is voluntary and will only be performed at selected sites. Additional time points may not be collected depending on the status of the Screening/Baseline biopsy sample. Repeat Screening/Baseline biopsy samples may be collected if the initial sample is not of sufficient quality.
- y Patients enrolling in the open-label extension study (ALN-TTRSC-006) will not need to complete the Month 19 visit. For these patients, Month 18 assessments will constitute the End of Study assessments.
- z Serum chemistry (including LFTs) and coagulation tests are to be performed at Week 17 and Week 21.

aa Serum SPEP with IFE, urine SPEP with IFE and serum FLC is to be performed at Screening/Baseline. If available, documented local results obtained within 1 year of Screening/Baseline may be used to fulfill this requirement.

bb These assessment will only be performed for patients enrolling in the ALN-TTRSC-006 study.

TABLE OF CONTENTS

STUDY	SYNOPSIS	3
TABLE (OF CONTENTS	15
LIST OF	TABLES	20

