7.3. Efficacy Assessments

7.3.1. Six-Minute Walk Test

The 6-MWT will be administered by staff trained in the procedure included in the Site Operation Manual. The staff administering the 6-MWT will be different from the Investigator or designee managing the care of the patient.

The 6-MWT will be performed to assess functional exercise capacity and will include pre- and post-walk assessment of O₂ saturation, blood pressure, heart rate, and the Borg scale rating for dyspnea and fatigue. The Screening/Baseline visit assessment will include a practice and an actual 6-MWT at least 1 hour apart and must be done within 28 days prior to randomization. The higher of the two values at Screening/Baseline visit will be used for eligibility purposes. At all other visits, the test should be performed only once at approximately the same time of the day. On dosing days, including Day 0, the 6-MWT should be performed prior to study drug administration. Patients who are hospitalized during the course of the study should wait at least two weeks after hospitalization before completing a 6-MWT assessment.

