6 DATA HANDLING

6.1 Time Points and Visit Windows

Day 1 will be defined as the day of first dose of study drug.

An evaluation date will be calculated relative to Day1 as follows:

- RelDay = (date of assessment date of first dose + 1) if collected after Day 1.
- RelDay = (date of assessment date of first dose) if collected prior to Day 1.

For analysis by visit, analysis windowing will be utilized for each scheduled visit such that unscheduled visits will also be considered. If there is more than one value within a visit window then the visit closest to the target day of the visit will be used in the analysis. If measurements are equally distant to the target day, then the later one will be used in the analysis. Details regarding the definition of the visit window will be summarized in a separate specifications document.

Baseline Definitions:

- For 6-MWD, baseline will be defined as the latest value prior to the first dose. If Day 1 assessment is not available, then the latest of the 2 screening 6MWD results will be selected to represent the baseline value for the patient in the analysis.
- For each of the PD parameters, baseline will be defined as the average of all measurements collected prior to the date of the first dose of study drug.
- For all other parameters, the baseline will be defined as the last assessment prior to the first dose
 of study drug.

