Sensitivity #2: Address influence of missing data

Complete Cases (CC) analysis will include all patients with non-missing 6-MWD results at 18 months. An ANCOVA model will be employed where the dependent variable is a change from baseline in 6MWD (meters) to month 18 with a covariate for treatment group. No imputation will be considered.

Below are additional descriptive analyses of each component of the co-primary analysis. These analyses will be unstratifed using the mITT population.

Time to death: The distribution of time from date of first dose of study drug to death for each treatment group will be generated using Kaplan-Meier (KM) plot. For each percentile (25th, 50th, 75th) if reached, an estimate of time of death from date of first dose and the associated 95% confidence intervals using Brookmeyer-Crowley methodology will be presented for each treatment group. The survival rates at 3, 6, 9, 12, 15 and 18 months for each treatment group will also be presented. Appendix I includes additional details regarding the definition for time to death.

Time to loss of ability to perform 6-MWD: Time from date of first dose to loss of ability to perform 6-MWD will be based on months 3, 6, 12 and 18 visits. The frequency and percentage of patients who lose the ability to walk will be presented at each analysis visit by treatment group. The cumulative number of patients and associated percentage in each treatment group who were unable to perform the 6-MWD up to month 18 will also be presented. In addition, there will also be a summary table and listing (overall and by visit) of the number (frequency) of patients that were unable to walk at the visit and the corresponding

Version: 1.0

Alnylam Protocol No. ALN-TTRSC-004

reasons why the patient was unable to walk. Appendix I includes additional details regarding definition of time to loss of ability to perform 6-MWD.

Change in 6-MWD from baseline: Descriptive statistics of observed change in 6-MWD (meters) from baseline to analysis visits at 3, 6, 12 and 18 months will be generated. Appendix I includes additional details regarding the definition of change in 6-MWD from baseline.

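### SAP Appendix I judges a new walking aid or more oxygen against the screening visits but walk distance against the Day 0 baseline, so a change before the first dose can be scored as an on-study loss of ability

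*SAP*

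**What the plan says.** The primary 6-MWD analysis compares pairs of patients on time to death (Step 1), then time to loss of ability to perform the walk (Step 2), then change in distance (Step 3).

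- **Step 2 (SAP Appendix I).** Two of the three triggers for loss of ability refer back to screening: "A patient could not perform the test without an additional walking aids compared to the walking aid used at the screening visits" and "A patient could not perform the test without an increase in oxygen flow compared to the oxygen flow used at the screening visits".
- **Step 3 (SAP Appendix I and Section 6.1).** Distance is measured from the Section 6.1 baseline: "For 6-MWD, baseline will be defined as the latest value prior to the first dose". Screening is only the fallback: "If Day 1 assessment is not available, then the latest of the 2 screening 6MWD results will be selected".
- **Day numbering.** SAP Section 6.1 states that "Day 1 will be defined as the day of first dose of study drug", so SAP Day 1 is the protocol's Day 0.
- **Separate tests.** Protocol Section 7.3.1 requires a walk before the first dose: "On dosing days, including Day 0, the 6-MWT should be performed prior to study drug administration". The two screening walks come earlier; under Protocol Table 1-1, footnote t, "both tests must be completed within 28 days of Day 0".
- **Dating of loss.** SAP Section 7.6.1.2 says that time to loss "will be based on months 3, 6, 12 and 18 visits". Appendix I counts time from the first dose and dates the loss at the visit from which ability was not regained. A note adds that anyone able to perform the walk at Month 18 is censored.

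**The concern.** Two steps of one co-primary endpoint use different reference tests, and no rule covers a change of aid or oxygen that is already present at the Day 0 walk. Step 2 can therefore record as an on-study event something that happened before treatment, and can miss a deterioration that happened after it. Step 2 is settled before distance is considered. A patient flagged at Month 3 loses to every patient in the stratum who is known to have kept the ability at least that long, if Step 1 did not separate them. This holds even if the flagged patient walks as far as at baseline, with the same support as at baseline.

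**Working it through.** **1. The rules applied to three patients.** Here the Month 18 note is read strictly, so that a walk needing the added support does not count as able.

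| Patient | Screening | Day 0 walk | Later walks | Change since baseline walk | Step 2 as written |
|---|---|---|---|---|---|
| A | no aid | cannot walk without an aid | same aid still needed | none | loss, dated Month 3 |
| B | aid | no aid | same aid needed again | worse | not flagged |
| C | no aid | not done | aid needed | worse | loss, correctly |

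A and B are misclassified relative to baseline. C is not, because the distance baseline then falls back to screening as well. The same table applies to oxygen flow.

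**2. The Month 18 note.** If any completed walk counts as able, patient A is censored at Month 18 and is compared on distance. The mismatch then matters only for patients without a Month 18 walk. For example, if A walks with the aid through Month 12 and cannot walk at all at Month 18, the loss is dated Month 3 instead of Month 18. If able means without the added support, A is a loss from Month 3. The SAP does not say which reading applies.

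**3. The plan's own power figure.** Inputs from SAP Section 2.3: 120 against 60 patients, a difference of 0.55 SD, deaths of 13% and 20% by 18 months, two-sided 0.05, power about 90%.

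- Two-mean formula ignoring deaths: 0.55/√(1/60 + 1/120) = 0.55/0.1581 = 3.48; Φ(3.48 − 1.96) = 93.6%.
- Simulated joint rank test, unstratified. Deaths are exponential and ranked by time; survivors are ranked by normally distributed change. The score is U = 2 × rank − (N + 1), T is the sum of U over the active arm, V = n₁n₀/(N(N − 1)) × ΣU², and the test rejects if |T|/√V > 1.96. Power is 88.3% at 0.55 SD (40,000 runs) and 89.0% at 39/70 = 0.557 SD (20,000 runs).
- Dropout: 180/0.9 = 200.

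The stated 90% is reproduced to within 2 points.

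**4. Effect of the screening reference.** The documents give no frequency for pre-dose changes, so a share q in each arm is assumed. Affected survivors are ranked above deaths and below all other survivors, and by distance among themselves. Using the Day 0 reference corresponds to q = 0. There were 40,000 runs for each column; the type I column sets deaths at 20% in both arms and no difference in distance.

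| q (assumed) | Power | Type I error |
|---|---|---|
| 0 | 88.3% | 4.9% |
| 1% | 87.5% | 4.9% |
| 2% | 86.4% | 4.8% |
| 5% | 83.0% | 4.9% |
| 10% | 77.2% | 5.0% |

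With four non-prognostic strata (the SAP stratifies on two two-level factors; 20,000 runs), power is 86.7%, 85.6% and 84.6% at q = 0, 1% and 2%, again a loss of about 1 to 2 points. For scale, 1% to 2% of 200 patients is 2 to 4 patients.

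The simulation assumes that every affected patient stays affected and that the Month 18 note is read strictly. Both assumptions make the loss larger. It also assumes no other loss of ability on study, because the documents give no rate.

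**The case against.** The case against giving this much weight is substantial, and most of it stands.

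- **Month 18 note.** A reader might infer that anyone who takes up a cane by Day 0 and keeps it is certain to be scored as lost from Month 3. The documents do not support that certainty: on one natural reading, the note censors exactly that patient. The note does not remove the problem, because its meaning is open and it does not reach patients without a Month 18 walk.
- **Use is not inability.** The bullets require that the patient could not do the test without the extra support, and a loss counts only from the visit after which ability is not regained. A cane carried for convenience, or a passing need, does not qualify.
- **Eligibility.** Exclusion criterion 8 bars a PND score above 2, and Protocol Appendix 3 places walking with one stick at stage IIIA. Eligibility is rechecked on Day 0. This removes many aid users. It does not cover oxygen, and an aid needed for a non-neuropathic reason might not be scored. The PND score itself is scheduled before treatment only at screening.
- **Bias.** A reader might infer that the rule favours one arm. The change precedes the first dose in a randomized, blinded trial, so no systematic imbalance is expected, and simulated type I error does not move. A chance imbalance of a few patients is possible but is part of ordinary sampling error.
- **Two screening walks.** A reader might infer that the reference is not unique because there are two screening tests. They are a practice and an actual test within the Screening/Baseline assessment, at least an hour apart; nothing suggests that support would differ between them.
- **Other safeguards.** Appendix I promises a review of walk data before database lock, but states no rule for this case. The MMRM and complete-case sensitivity analyses do not use Step 2, but they are not the primary test.

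**Conclusion.** The mismatch is real and should be corrected, but its consequence is modest. Step 2 and Step 3 do not share a baseline, and the literal text can misclassify a persistent change that occurs between screening and Day 0, in either direction. The number of patients affected cannot be derived from the documents. The gap of at most 28 days, the PND exclusion, and the requirement of optimally managed heart failure with no CV hospitalization during screening all point to a small share. At an assumed 1% to 2% in each arm, the cost is about 1 to 2 points of power. The larger losses in the table need shares of 5% to 10%, which nothing in the documents suggests. The result is noise in a co-primary endpoint, not systematic bias, and it is unlikely on its own to decide the trial.

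**What to change.** Two edits to SAP Appendix I:

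1. In both Step 2 bullets, change the reference from the screening visits to the 6-MWT that supplies the baseline value in Section 6.1. If aid or oxygen data from the Day 0 walk are missing, fall back to the latest screening test.
2. In the Month 18 note, state that being able to perform the walk is judged by the same Step 2 definition, so that the aid and oxygen triggers are applied consistently at that visit.

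The cost is a few words, and SAP Section 7.8 already foresees an update for the futility criteria that could carry them. There is one small downside. The current rule needs aid and oxygen flow at screening and after baseline, not on Day 0, and the protocol's list of 6-MWT assessments names neither. The sponsor must confirm that the CRF records both at the Day 0 walk. If it does not, the fallback leaves those patients on the screening reference, and the SAP should say so.

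### Step 2 of the 6-MWD joint rank test times loss of ability by analysis visit but censors walkers by test date, so some Month 18 walkers are undecided against a Month 18 non-walker

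*SAP*

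**What the plan says.** Protocol 9.2.3.1 orders the pairwise comparison as death, then inability to perform the test, then change in distance. SAP Appendix I turns the second comparison into a rule with two times.

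- **Loss time.** "The time of loss of ability to perform 6-MWD will be based upon the analysis visit". The tie rule repeats the visit scale: a pair in which both lost ability is decided if "there is no tie in the time to loss (scheduled visit"). SAP 7.6.1.2 names the visits as Months 3, 6, 12 and 18.
- **Censoring time for a walker.** A calendar figure: "date of the latest 6MWD – date of first dose +1)/30.4".
- **Decision.** The pair is decided if the loss time is at or below the walker's censoring time. It is inconclusive if "the time of the patient who lost the ability to walk > the time of the patient who did not lose the ability".
- **Limit and note.** "Time from first dose to loss of ability will allow values up to Month 18 analysis visit". Also: "Any patient that is able to perform the walk at Month 18 visit will be considered a censored patient".
- **Death in the Month 18 window.** If a patient walked at Month 18 and died within that window, "the patient will be considered unable to perform 6-MWD at month 18".

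Step 1 of the same appendix does not mix scales. Death time is a date difference, and so is censoring time: "date of last study visit –date of first dose of study drug+1)/30.4".

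The text does not say what number a Month 18 loss takes, or that a Month 18 walker is censored at 18.

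**The concern.** If one patient completes the Month 18 walk and another cannot, the protocol's ordering makes the first the better outcome. Under the printed rule that depends on the day the walker happened to be tested. A test a little early, or exactly on target under one coding, gives a censoring time below the loss time, and Step 2 returns no decision.

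The pair then goes to Step 3, which uses the latest visit at which both have a distance. That is normally Month 12 or earlier, because the non-walker usually has no Month 18 distance. If the non-walker had the better change at that visit, the non-walker wins the pair. The rule belongs to a co-primary analysis, and two programmers could code it differently without departing from the text.

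**Working it through.** **Plan's own figure.** SAP 2.3 gives about 90% power for 120 versus 60 patients, a 0.55 SD effect, deaths of 13% versus 20% and two-sided 0.05. A simulated, unstratified joint rank test (20,000 runs) gives:

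- 88.2% with 13% deaths on active.
- 89.4% with a hazard ratio of exactly 0.6, where active deaths are 1 − 0.8^0.6 = 12.5%.
- 89.9% with that hazard ratio and 39/70 = 0.557 SD.

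The figure is reproduced. Four strata give 86.3–88.3%. No loss of ability was modelled, because the plan gives no rate, so this says nothing on the present point.

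**Inputs for the timing check.** Protocol Table 1-1 places the walk tests at Weeks 13, 26, 52 and 78, which are 91, 182, 364 and 546 days after first dose. Footnote d allows ±14 days for assessments.

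**Censoring time on the target day, (days + 1)/30.4:**

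- Month 3: 92/30.4 = 3.026
- Month 6: 183/30.4 = 6.020
- Month 12: 365/30.4 = 12.007
- Month 18: 547/30.4 = 17.993

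Over ±14 days the Month 18 value runs from 533/30.4 = 17.53 to 561/30.4 = 18.45. The first day reaching 18 is one day after target (548/30.4 = 18.03). The Month 18 limit is a ceiling and cannot raise 17.53 or 17.99.

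**Share of Month 18 walker versus Month 18 non-walker pairs left undecided at Step 2.** Visit-day distributions are assumed. The last three columns use an SD of 5 days, truncated at ±14.

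| Loss coded as | Undecided if walker tested | Uniform ±14 days | Centred | 5 days late | 5 days early |
|---|---|---|---|---|---|
| 18 | on or before Week 78 | 15/29 = 51.7% | 54% | 19% | 86% |
| Target day, 17.993 | before Week 78 | 14/29 = 48.3% | 46% | 14% | 81% |
| Both times on visit scale | never | 0% | 0% | 0% | 0% |

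A third coding takes the non-walker's own visit date. Both times are then dates, so no scales are mixed. Differences in visit day still leave 406/841 = 48.3% of pairs undecided under uniform visits, or 315/841 = 37.5% if both times are capped at 18.

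**Other visits.** A walker last tested at Month 3, 6 or 12, compared with a patient lost at that same visit, is undecided if tested before the target day (14 of 29 window days). A loss at Month 3, 6 or 12 against a Month 18 walker is always decided, since 12 is below 17.53.

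**How many pairs.** With four equal strata of 30 and 15 patients there are 4 × 30 × 15 = 1,800 between-arm pairs. The simulation (8,000 runs per scenario) used the plan's deaths, SD and effect. It assumed centred visits, a Month 12–18 correlation of 0.7, and loss striking the lowest Month 18 values. Figures are for loss coded 18, then target day.

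- About 6 patients first unable at Month 18: 63.3 and 54.0 pairs undecided (63.3/1,800 = 3.5%; 54.0/1,800 = 3.0%), with 5.6 and 4.8 reversed. Power is 87.8% under both, against 88.2% on a common scale.
- About 12 patients: 119.0 and 101.4 undecided (6.6% and 5.6%), with 13.1 and 11.2 reversed. Power is 87.5% and 87.6%, against 88.3%.
- Loss unrelated to distance: power is 86.1% and 85.8% against 83.6% (about 6 patients), and 84.4% and 83.9% against 79.1% (about 12).
- With no treatment effect, rejection is 4.6–5.3% for every rule.

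A second set of simulations, with assumed permanent-loss rates of 10–30% and loss coded 18, put about 3–7% of between-arm pairs in the affected group. Power under the printed rule against the common scale was 86% vs 85%, 83% vs 81%, 79% vs 76% and 70% vs 63%.

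**The case against.** The strongest objection is that the printed text may not be the whole rule. In this copy the step list in SAP 7.6.1.1 stops after its introduction, the Appendix II computational procedure is absent, visit windows are left to a separate specification (SAP 6.1), and a page after the co-primary steps of Appendix I may also be absent. Any of these could give visits their numbers. This stands: the point concerns what Appendix I prints and cannot show that the plan as a whole lacks a consistent rule.

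It can also be said that the limit on times and the note on Month 18 walkers, read together, imply censoring at 18. That is a sensible intention, and if it is meant the Month 18 problem disappears. But the note gives a status without a time, and the only time printed for a censored patient is the date formula.

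A reader might infer that the mismatch exists however loss is coded. It does not: with the non-walker's own date, an undecided pair is ordinary date censoring, as in Step 1. A reader might also infer from the 52% that half the comparisons fail. That share applies only to pairs of a Month 18 walker and a patient first unable at Month 18.

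The SAP is to be finalised before database lock (protocol 9.2), and Appendix I promises a pre-lock look at the walk data for unexpected scenarios. Both leave room for a correction, but neither sets the time scale.

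**Conclusion.** The point holds as a minor correction to a co-primary rule. As printed, the walker's visit day can override the protocol's ordering: about half of the specific pairs are undecided at Step 2 if visits are uniform over ±14 days and a Month 18 loss is coded 18 or at the target day. The share moves between 14% and 86% if visits run five days late or early. In the first set of simulations 3.0–6.6% of between-arm pairs are undecided and well under 1% are reversed.

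A reader might go further and infer lost power, bias or an inflated error rate. The material does not support that. Power falls by less than one point when loss tracks distance. It is higher under the printed rule when loss is unrelated to distance, and in all four scenarios of the second set. Type I error stays near 5%, and nothing shows one arm favoured.

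The numbers first unable, the visit-day spread and the correlation are assumptions, because the documents give none. The reason to act is that the ordering is unintended and the coding is open. Across the two visit-type codings, own-date coding capped at 18 and the common scale, at least one changed the verdict at 0.05 in 0.5–2.6% of simulated trials when loss tracked distance, and in 4.2–7.2% when it did not.

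**What to change.** Before unblinding, state in SAP Appendix I that both Step 2 times take the values 3, 6, 12 or 18:

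- Loss time is the analysis visit from which the patient was unable to perform the test and never regained the ability.
- Censoring time is the last analysis visit with a completed test that does not meet the loss definition. A patient who walks at Month 18 without meeting that definition is censored at 18.
- Keep the existing rule for death within the Month 18 window.

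Then confirm that SAP 7.6.1.1, Appendix II and the visit-window specification use the same definition. The specification should also say whether a late early-termination test can fill the Month 18 visit, since that patient would then be censored at 18. If those texts already put both times on one scale, only the date formula in Appendix I needs correcting.

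The cost is about two sentences and a small programming check. No extra data are needed.
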